3 ENDPOINT ANALYSIS

3.1 Primary Safety/Effectiveness Endpoints

Primary Effectiveness Endpoint: The distance between the posterior prostatic capsule and anterior rectal wall post SpaceOAR hydrogel administration.

Measurement: The distance between the posterior prostatic capsule and anterior rectal wall is measured on the axial image slice closest to halfway between apex and base, from posterior edge of prostate to inner rectal wall.

Primary Safety Endpoint: AEs related to SpaceOAR system and/or procedure within 30 days following procedure will be observed.

3.1.1 Hypothesis

This is a retrospective and prospective, single arm study with a performance goal approach for the primary effectiveness endpoint. The primary effectiveness endpoint is the distance between the posterior prostatic capsule and anterior rectal wall post SpaceOAR hydrogel administration. As this is real world study with less strict I/E criteria, the performance goal was set as 7.5mm. The choice of this performance criterion is based on the rationales that for the SpaceOAR EU pilot study, a creation of at least a 7.5mm space was considered clinical meaningful in the consultation with Augmenix's Scientific Advisory Board (a panel that consists of board-certified radiation oncologists). If the two-sided 95% Lower Confidence Interval (LCI) of distance calculated is greater than PG, the study primary effectiveness endpoint will be met.

3.1.2 Sample Size

The sample size for effectiveness endpoint was estimated based on the following assumptions:

- Confidence level ($1-\alpha$) = 0.975
- Expected distance between prostate and rectum: 13 mm
- Estimated standard deviation: 5.7 mm
- Power: 90%

The sample size is calculated according to below formula:

$$n = \frac{(Z_\alpha + Z_\beta)^2 \sigma^2}{\delta^2}$$

n is sample size, PG is assumed as 7.5mm, 13mm is the expected distance between prostate and rectum, $\delta = 5.5$ mm, $\sigma = 5.7$ mm, $\alpha = 0.025$, $\beta = 0.1$ (power=90%). Therefore, a sample size of 14 subjects will provide more than 90% power.

To account for potential missing data in this retrospective and prospective study, a final sample size will be up to 20 subjects.

3.1.3 Statistical Methods

Descriptive statistics (mean, median, SD, min and max) along with corresponding 95% confidence interval will be used to summarize the effectiveness endpoints, such as distance between the posterior prostatic capsule and anterior rectal wall post SpaceOAR hydrogel administration. One sample t-test will be used to calculate the p-value for

primary effectiveness endpoint. To summarize safety endpoint, AEs related to SpaceOAR system and/or procedure within 30 days will be tabulated with frequencies, percentages along with the 95% confidence intervals.

This study may allow explorative statistics based on collected data, including but not limited to: risk factors associated with functional failure.

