11.2. General Statistical Methods

11.2.1. Analysis Sets

This study is a retrospective and prospective, real world study, in which subjects who received the treatment of spaceOAR in hospital in BOAO will be enrolled. The efficacy analysis set includes subjects with available distance between prostate and rectum measured from MRI post procedure. The safety analysis set includes all subjects who have received treatment of SpaceOAR in hospitals in Hainan BOA.

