1.6 Follow-up schedule

Retrospective cohort: For those patients who had been injected with SpaceOAR hydrogel before study kick-off, relevant clinical data at baseline and procedure will be collected retrospectively, any AE at 30 days post procedure will be collected, if applicable.

Prospective cohort: For those patients who will be injected with SpaceOAR hydrogel, informed consent formed will be gained prospectively, follow up at 30 days will be conducted to assess any AEs.

The data collection schedule is shown in below table:

Procedure/Assessment	Before procedure	Procedure	Post procedure	30 days post procedure (± 7 days)
Informed consent [#]	X			
Demographics	X			
Physical assessment, including weight and height	X			
Clinical diagnosis and clinical stage of tumor, Gleason score	X			
Medical history (General disease, genitourinary history / treatment history)	X			
Questionnaires (IPSS, EPIC, QoL)	X			
Administration of SpaceOAR		X		
PSA	X			
CT&MRI [*]	X		X	
Concomitant medication		X	X	
Adverse event		X	X	X
Device Deficiency		X	X	X
PD [#]	X	X	X	X

Note:[#] only for patients enrolled prospectively;

^{*}MRIs conducted in other hospital are allowed, ie, MRI completed in 30 days before procedure and in 10 days after procedure will be allowed in this study. MRI is required for patients with prostate cancer who receive radiotherapy; technical success and distance between the prostate and rectum will be evaluated based on MRI image.

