3.2.2 Statistical Methods

The proportion of subjects who experiences a functional success will be summarized along with the 95% confidence interval (Clopper-Pearson Exact Method).

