4 GENERAL STATISTICAL METHODS

4.1 Analysis Sets

This study is a retrospective and prospective, real world study, in which subjects who received the treatment of SpaceOAR in hospital in BOAO will be enrolled.

The efficacy analysis set includes subjects with available distance measurement between prostate and rectum measured from MRI post procedure.

The safety analysis set includes all subjects who have received treatment of SpaceOAR in hospitals in Hainan BOAO.

All enrolled set: Retrospective subjects, who have already received the SpaceOAR treatment, are enrolled when they meet the inclusion criteria. Prospective subjects, who will receive the SpaceOAR treatment, informed consent will be performed for enrollment.

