4.2 Control of Systematic Error/Bias

All patients who receive the treatment of SpaceOAR in hospital in BOAO will be enrolled during the study period to minimize selection bias.

4.3 Method of handling missing, incorrect data (including subjects withdrawal and lost to follow-up) and unreasonable data

Missing data will be excluded for primary analysis in this small sample size study. Incorrect and unreasonable data will be clarified before database lock. Imputation with mean or median where applicable for continuous variable, and tipping point analysis where applicable for categorical variable might be conducted for sensitivity analysis. Visit-wise mean and LOCF imputation methods will be used for missing values.

Missing Event Dates Considerations:

For adverse events with missing event date (i.e., mm/dd/yyyy), the safety and/or data management representatives will query sites for missing data. In the event that the date for adverse event is missing at the time of analysis, please reference Section 7.4 for the missing/partial date handling rules.

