5.2.5 Analysis of Adverse and Serious Adverse Events

Frequency of site reported Serious adverse events and Non-serious adverse events associated with the study device will be summarized. The events will be summarized by MedDRA system organ class and MedDRA system preferred terms with event counts and proportions. A listing based on all site reported adverse events with seriousness, relationships and duration days will be created. Similarly, a listing for all anticipated/unanticipated adverse device events with seriousness and duration from onset date will be also produced.

For calculating events and rates, ‘Events numbers’ are total number of episodes for each type of event among all subjects. ‘Rate of Subjects with Event’ numbers are percent of subjects who experienced one or more episodes of the event. ‘Events’ numbers for “TOTAL” are the sum of the individual event category totals. ‘Rate of Subjects with Event’ numbers for “TOTAL” is the percent of subjects who experienced at least one adverse event.

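### The primary safety percentage pools two cohorts whose described 30-day AE ascertainment differs, and no rule for this endpoint says how unknown status is counted

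*SAP*

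**What the plan says.** **Analysis.** Related AEs within 30 days are a primary endpoint (Protocol 6.2.1.2, SAP 3.1). SAP 3.1.3 plans that "AEs related to SpaceOAR system and/or procedure within 30 days will be tabulated with frequencies, percentages along with the 95% confidence intervals". That sentence names no analysis set, cohort or interval method. The only safety set is in SAP 4.1: "The safety analysis set includes all subjects who have received treatment of SpaceOAR in hospitals in Hainan BOAO"; Protocol 11.2.1 says the same. SAP 5.2.5 defines its AE rates likewise: they "numbers are percent of subjects who experienced one or more episodes of the event". It gives no split by cohort and no condition that status is known. An interval method is named only for functional success, in SAP 3.2.2: "The proportion of subjects who experiences a functional success will be summarized along with the 95% confidence interval (Clopper-Pearson Exact Method".

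**Prospective cohort.** Protocol 10.4.2 describes a day-30 telephone visit that asks about health status and AEs. Protocol 9.3 adds a tracing rule of at least three attempts, marked as prospective only.

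**Retrospective cohort.** Protocol 10.4.1 plans retrospective collection of AEs within 30 days. SAP 1.6 says "any AE at 30 days post procedure will be collected, if applicable". In the data collection schedule the day-30 AE mark does not carry the prospective-only symbol. No call or other contact is described. Besides the inclusion criteria, entry needs a complete procedure record (Protocol 9.1). Protocol 14 foresees missing retrospective data and does not treat them as deviations.

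**General rules.** SAP 4.3 excludes missing data from the primary analysis and adds that "tipping point analysis where applicable for categorical variable might be conducted for sensitivity analysis". SAP 7.3, after a sentence on baseline categorical variables, bases denominators on patients who complete the visit.

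**The concern.** An all-treated percentage is sound when every subject's outcome is known. Here a prospective subject without an AE has normally been asked, while a retrospective subject without an AE may only have a record that stops before day 30. Both enter the denominator, and both look event-free in the numerator. An absent AE record is nowhere defined as missing, so the default pulls the rate down.

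The same gap leaves the number itself open. Two programmers following the SAP could use all treated subjects, subjects with known status, or subjects who completed a visit.

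No hypothesis or performance goal is attached to this rate, so the stake is how the safety result reads. That still matters: the data are meant to support approval in China (Protocol 17.4), there is no comparator, and there is no events or data monitoring committee (Protocol 20.2). SAP 5.2.4 (30-day compliance) and SAP 5.2.5 (AE listing) show part of the picture, but neither is specified by cohort.

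**Working it through.** The documents state no expected rate or precision for the safety endpoint, so there is no plan figure to reproduce. The one input taken from them is the ceiling of 20 subjects (SAP 3.1.2). Everything else below is assumed and shown as a range.

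**1. Attenuation of the pooled rate**

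Let r be the retrospective share, c the fraction of true related AEs captured in the retrospective cohort, and cp the same fraction in the prospective cohort. Assume the true rate is equal in both cohorts and that unascertained subjects count as event-free. Then

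reported rate / true rate = (1 − r) × cp + r × c

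| r | c | cp = 100% | cp = 90% |
|---|---|---|---|
| 25% | 90% | 0.75 + 0.225 = 0.975 | 0.90 |
| 25% | 50% | 0.75 + 0.125 = 0.875 | 0.80 |
| 50% | 90% | 0.50 + 0.45 = 0.95 | 0.90 |
| 50% | 50% | 0.50 + 0.25 = 0.75 | 0.70 |
| 75% | 90% | 0.25 + 0.675 = 0.925 | 0.90 |
| 75% | 50% | 0.25 + 0.375 = 0.625 | 0.60 |

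With c = cp = 100% the ratio is 1. At a ratio of 0.75, a true 20% reads 15% and a true 5% reads 3.75%. With cp = 100%, the expected number of missed subjects among 20 is 20 × p × r × (1 − c), where p is the true rate. For r = c = 50% this is 1.0 at p = 20% and 0.25 at p = 5%.

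**2. Precision when no event is seen**

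The exact upper 95% limit for 0/n is 1 − 0.025^(1/n):

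- 0/20: 16.8%
- 0/18: 18.5%
- 0/15: 21.8%
- 0/10: 30.8%

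The choice of interval matters too: a Wald interval for 0/20 runs from 0% to 0%.

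**3. One documented related AE among 20 treated**

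Clopper-Pearson 95% limits are the 0.025 quantile of Beta(x, n − x + 1) and the 0.975 quantile of Beta(x + 1, n − x).

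| Unascertained | All treated | Known status only | Each unascertained counted as an event |
|---|---|---|---|
| 2 | 1/20 = 5.0% (0.1 to 24.9) | 1/18 = 5.6% (0.1 to 27.3) | 3/20 = 15.0% (3.2 to 37.9) |
| 5 | 1/20 = 5.0% (0.1 to 24.9) | 1/15 = 6.7% (0.2 to 31.9) | 6/20 = 30.0% (11.9 to 54.3) |
| 10 | 1/20 = 5.0% (0.1 to 24.9) | 1/10 = 10.0% (0.3 to 44.5) | 11/20 = 55.0% (31.5 to 76.9) |

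The all-treated column does not change with the number unascertained, so a reader who sees only that column cannot tell how much follow-up lies behind it.

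**The case against.** **Collection is planned for both cohorts.** This stands. The schedule, Protocol 10.4.1 and SAP 1.6 all provide for retrospective 30-day AEs, and Protocol 18.4 sets reporting timelines for them. A reader might infer from the qualifiers attached to retrospective AEs that weaker capture is intended. The documents do not support that: Protocol 10.4.2 attaches the same kind of qualifier to prospective AEs, and its natural sense is that an event is recorded if one occurred. What remains is that no method of contact is described for retrospective subjects.

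**Rules for missing data exist.** Also true, so it would be wrong to say that the SAP is silent. But excluding missing data points to a known-status denominator, and the visit-completion sentence points to another. Both sit awkwardly with an all-treated set, and retrospective subjects have no described day-30 contact to complete. A reader might also infer from "Visit-wise mean and LOCF imputation methods will be used for missing values" that a no-AE status would be carried forward to day 30. That is speculative: AEs are event records rather than repeated visit values, and nothing applies this sentence to them.

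**Some AE rules are already conservative.** SAP 7.4 gives an event with no onset date the procedure date, so it falls within 30 days. Protocol Table 18-2 classes unassessable relatedness as possibly related. Both limit under-counting of reported events. Neither addresses subjects for whom it is unknown whether an event occurred.

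**The trial is small and the endpoint descriptive.** This is fair. In the middle scenario at a true 5%, a quarter of one subject is missed, which is small beside an interval of 0.1% to 24.9%. It argues for a light remedy, not for leaving the denominator and follow-up unstated.

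**Conclusion.** The point holds as a recommended change to the analysis. The primary safety percentage combines cohorts whose described ascertainment differs, and no rule specific to this endpoint says how unknown 30-day status is counted. If retrospective capture is incomplete and unascertained subjects stay in the denominator as event-free, the rate and its interval are biased low.

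The size cannot be derived from the documents. For a retrospective share of 25% to 75% and retrospective capture of 50% to 90%, the reported rate is 0.625 to 0.975 of the true rate with full prospective capture, and 0.60 to 0.90 with 90% prospective capture. These figures rest on assumed shares and capture and on equal true rates in the two cohorts. They show what could happen; they do not show that retrospective AEs will in fact be missed. At full capture there is no bias. The effectiveness decision is unaffected.

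**What to change.** In SAP 3.1.3:

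1. Name the all-treated safety set as the denominator, keep every documented related AE within 30 days, and use the exact (Clopper-Pearson) 95% interval already chosen in SAP 3.2.2. This remains the main result.
2. Report the same rate with its exact interval separately for the prospective and retrospective cohorts.
3. Report by cohort how many subjects have documented 30-day status: either a related AE within 30 days, or a contact or record at day 30 or later showing none. Show last contacts on days 23 to 29 separately; they fall within the visit window (30 ± 7 days) but leave up to 7 days unobserved.
4. If any subject is unascertained, describe the all-treated rate as a lower bound in that respect and add a sensitivity analysis on subjects with known status. A worst-case analysis is optional.

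Two optional wording changes would help: say that the visit-completion sentence in SAP 7.3 and the imputation sentence in SAP 4.3 do not apply to AE rates, and reconcile SAP 1.1, which lists only baseline and procedure-day data for the retrospective cohort, with SAP 1.6.

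**Cost.** SAP text, cohort columns, and a last-contact date to take from records. Cohort intervals will be wide: 0/10 has an upper limit of 30.8%, against 16.8% for 0/20. The known-status rate may be biased upward, because a subject with an AE always counts as known and a late record may exist because of a problem. It should therefore stay a sensitivity result.

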3.2 Secondary Endpoints

Functional Success: Defined as creation of at least 7.5mm space between the posterior prostatic capsule and anterior rectum wall as assessed via comparative pre and post SpaceOAR hydrogel injection diagnostic quality MRI scans.

3.2.1 Hypothesis

No formal tests of hypotheses are proposed for secondary endpoints. No formal inferences are planned on the additional assessments.

3.2.2 Statistical Methods

The proportion of subjects who experiences a functional success will be summarized along with the 95% confidence interval (Clopper-Pearson Exact Method).

4 GENERAL STATISTICAL METHODS

4.1 Analysis Sets

This study is a retrospective and prospective, real world study, in which subjects who received the treatment of SpaceOAR in hospital in BOAO will be enrolled.

The efficacy analysis set includes subjects with available distance measurement between prostate and rectum measured from MRI post procedure.

The safety analysis set includes all subjects who have received treatment of SpaceOAR in hospitals in Hainan BOAO.

All enrolled set: Retrospective subjects, who have already received the SpaceOAR treatment, are enrolled when they meet the inclusion criteria. Prospective subjects, who will receive the SpaceOAR treatment, informed consent will be performed for enrollment.

4.2 Control of Systematic Error/Bias

All patients who receive the treatment of SpaceOAR in hospital in BOAO will be enrolled during the study period to minimize selection bias.

4.3 Method of handling missing, incorrect data (including subjects withdrawal and lost to follow-up) and unreasonable data

Missing data will be excluded for primary analysis in this small sample size study. Incorrect and unreasonable data will be clarified before database lock. Imputation with mean or median where applicable for continuous variable, and tipping point analysis where applicable for categorical variable might be conducted for sensitivity analysis. Visit-wise mean and LOCF imputation methods will be used for missing values.

Missing Event Dates Considerations:

For adverse events with missing event date (i.e., mm/dd/yyyy), the safety and/or data management representatives will query sites for missing data. In the event that the date for adverse event is missing at the time of analysis, please reference Section 7.4 for the missing/partial date handling rules.

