10.4.2. Prospective cohort

For subjects who have been pathologically confirmed prostate cancer with clinical stage T1-T2, will receive the treatment of spaceOAR in hospital in BOAO. The radiotherapy plan will be made by radiotherapist according to clincial guideline and conditions of subjects.

- 1) Informed consent

Study objective, schedule and visits will be informed to subjects fully, and the ICF will be signed voluntarily.

2) Before procedure

The data below will be collected, such as demographics, physical assessment (height, weight), clinical diagnosis and clinical stage, Gleason score, PSA, CT, MRI and other related examinations, medical history, urinary history and surgery history etc. IPSS score will be collected, if any, and questionnaires of EPIC and quality of life (EQ-5D-5L) will be completed. (Clinical diagnosis and clinical stage, Gleason score, CT and MRI from other hospital within 30 days before procedure are allowed.)

3) Procedure

According to regulations of licenced medical device in Hainan, subjects will go to BOAO to receive treatment of SpaceOAR. SpaceOAR is injected between the prostate and rectum via TRUS .

All administration of SpaceOAR hydrogel will be conducted by trained urologists at the hospital in Boao.

Procedure information will be collected, such as anesthesia, SpaceOAR dosage, intraoperative device usage, device defects (if any), adverse events, complications, etc.

4) Post procedure

CT and MRI will be conducted in 10 days post procedure. AE and device deficiency, as applicable, will be assessed. CT and MRI will be conducted for all subjects to complete radiotherapy planning. MRI in other hospital will be allowed to avoid duplication assessment.

5) 30 days follow up visit post procedure

This visits will be conducted via phone, health status and concommit medication will be inquired, AE and device deficiency (if any) will be assessed and collected.

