11.2.2. Control of Systematic Error/Bias

All patients who receive the treatment of SpaceOAR in hospital in BOAO will be enrolled at a given time, no cherry-pick patients and data to reduce select bias.

11.2.3. The method of handling missing, incorrect data(including subjects withdrawal and lost to follow-up) and unreasonable data

Missing data will be excluded for primary analysis in this small sample size study. Incorrect and unreasonable data will be clarified before database lock. Imputation where applicable for continuous variable, and tipping point analysis where applicable for categorical variable might be conducted for sensitivity analysis.

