All deviations from the investigational plan, with the reason for the deviation and the date of occurrence, must be documented and reported to the sponsor using EDC. Sites may also be required to report deviations to the EC, and the regulatory authority, per local guidelines and national/government regulations.

Deviations will be reviewed and evaluated on an ongoing basis and, as necessary, appropriate corrective and preventive actions (including but not limited to EC/regulatory authority notification, site re-training, or site discontinuation/termination) will be put into place by the sponsor.

Considering that this study is a prospective and retrospective, real world study which is based on the 'pilot program' of licensed medical device, only collecting data, no intervention.

For data retrospectively collected, there is an chance of missing data, so missing data and undo test is not deemed to be deviations.

For prospective enrolled subjects who has signed ICF, Deviations must be recored, including but not limited to informed consent, inclusion criteria, follow-up visit etc.

15. Compliance

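### SAP 4.3 ends with an unscoped instruction to use visit-wise mean and LOCF imputation; it contradicts the complete-case rule, and neither method tests the distance endpoint usefully, even as a sensitivity analysis.

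*SAP*

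**What the plan says.** SAP 4.3 makes three statements about missing values in one paragraph:

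- Primary analysis: "Missing data will be excluded for primary analysis in this small sample size study".
- Sensitivity analysis, optional: "Imputation with mean or median where applicable for continuous variable, and tipping point analysis where applicable for categorical variable might be conducted for sensitivity analysis".
- Closing sentence, mandatory and without scope: "Visit-wise mean and LOCF imputation methods will be used for missing values".

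Protocol 11.2.3 has the same exclusion rule and the optional sentence ("Imputation where applicable for continuous variable, and tipping point analysis where applicable for categorical variable might be conducted for sensitivity analysis"), but names neither visit-wise mean nor LOCF. The efficacy set in SAP 4.1 is closed to missing distances: "The efficacy analysis set includes subjects with available distance measurement between prostate and rectum measured from MRI post procedure". Protocol 11.2.1 agrees.

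The data collection schedule (Protocol Table 10-1, SAP 1.6) has one MRI before and one after the procedure. For the prospective cohort, Protocol 10.4.2 says "CT and MRI will be conducted in 10 days post procedure", and the 30-day visit is by telephone. Success is declared if the lower limit of the two-sided 95% interval for the mean distance exceeds 7.5 mm (SAP 3.1.1).

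**The concern.** Read literally, the closing sentence requires imputation that the first sentence rules out and the second leaves optional. It also adds LOCF, which the second does not list. In the efficacy set there is nothing to impute, because only subjects with a measured post-procedure distance belong to it.

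The more important question is whether these methods would tell the reader anything if used as sensitivity analyses for the distance. Missing scans are foreseen. Enrolment goes up to 20, against 14 needed, to cover missing data (SAP 3.1.2), and Protocol 14 says "For data retrospectively collected, there is an chance of missing data, so missing data and undo test is not deemed to be deviations". With success resting on one confidence limit, the reader needs to know how much worse the missing distances would have to be to overturn it. Mean filling and LOCF do not answer that. The loose wording also leaves room to argue, once data are seen, that a filled-in data set was always intended as the main one.

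**Working it through.** **Inputs.** Mean 13 mm, SD 5.7 mm, performance goal 7.5 mm, one-sided alpha 0.025, 14 evaluable, up to 20 enrolled (SAP 3.1.2); one-sample t-test (SAP 3.1.3). The documents give no expected number of missing scans. I use m = 2, 3, 4 and 6 of 20, with m = 5 added for LOCF; 6 is the most that the margin from 20 to 14 covers. They also give no pre-injection distance, so I assume 0 to 5 mm with SD 2.0. Within that range, 1.6 ± 2.0 mm is the pivotal-study control-group figure (Protocol 4.1), used as a proxy.

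**The plan's own figure.** The printed formula gives (1.960 + 1.282)² × 5.7² / 5.5² = 11.29, rounded up to 12. With the t-test, exact power is 86.0% at 12, 89.1% at 13 and 91.5% at 14, so the stated 14 with more than 90% power is sound.

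**Mean filling.** Let n = 20 − m be the number observed.

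- Complete-case lower limit: 13 − t(0.975, n−1) × 5.7/√n.
- After filling, the SD falls to 5.7 × √((n−1)/19), and the lower limit is 13 − 2.093 × that SD/√20.
- If filled data drove the decision, type I error = P(t with n−1 df > 2.093/k), where k = complete-case SE / filled SE.

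| Missing | Complete-case SE | Complete-case limit (mm) | Filled SE | Filled limit (mm) | k | Type I error if filled data decide |
|---|---|---|---|---|---|---|
| 2 | 1.344 | 10.17 | 1.206 | 10.48 | 1.114 | 3.9% |
| 3 | 1.382 | 10.07 | 1.170 | 10.55 | 1.182 | 4.8% |
| 4 | 1.425 | 9.96 | 1.132 | 10.63 | 1.258 | 5.8% |
| 6 | 1.523 | 9.71 | 1.054 | 10.79 | 1.445 | 8.6% |

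The mean is unchanged, while both the SE and the critical value shrink. The filled limit is therefore always the higher one, and mean filling can turn a fail into a pass but never the reverse.

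At SD 5.7, the smallest observed mean that passes is 7.5 plus the half-width:

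- 4 missing: 10.54 mm under exclusion, 9.87 mm after filling.
- 6 missing: 10.79 mm under exclusion, 9.71 mm after filling. (The match with the limits in the last row of the table is a coincidence: the two half-widths happen to sum to almost 5.5 mm.)

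Any observed mean between the two values fails by complete case and passes after filling.

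**LOCF.** The only earlier distance is the pre-procedure one, so each missing value becomes the un-spaced gap, with mean b. Pooled mean = (13n + bm)/20. Pooled sum of squares = (n−1) × 5.7² + (m−1) × 2.0² + (nm/20)(13 − b)².

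Example, m = 6 and b = 1.6: the mean is (182 + 9.6)/20 = 9.58. The sum of squares is 422.4 + 20 + 545.8 = 988.2, so the SD is √(988.2/19) = 7.21. The lower limit is 9.58 − 2.093 × 7.21/√20 = 6.20 mm.

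| Missing | Limit, b = 0 (mm) | Limit, b = 1.6 (mm) | Limit, b = 5 (mm) | Gap at which the limit is 7.5 mm |
|---|---|---|---|---|
| 2 | 8.55 | 8.84 | 9.42 | none in range; passes |
| 3 | 7.73 | 8.14 | 8.98 | none in range; passes |
| 4 | 6.94 | 7.47 | 8.55 | 1.69 mm |
| 5 | 6.18 | 6.83 | 8.14 | 3.32 mm |
| 6 | 5.46 | 6.20 | 7.74 | 4.46 mm |

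With the pivotal-study values (12.58, SD 3.88) the pattern is the same: about 7.1 to 8.9 mm with 4 missing and 5.6 to 8.0 mm with 6.

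From identical observed data with 6 missing, the two named methods thus give 10.79 mm and, at the proxy gap, 6.20 mm. One is falsely precise and the other is a single fixed extreme.

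**The case against.** The best defence is that the primary analysis is already settled. Both documents exclude missing data and both define the efficacy set by an available measurement. The closing sentence follows directly on the sensitivity sentence and may simply expand it. That is probably the intent, and I accept complete case as the likely primary analysis. The type I error figures are therefore conditional on a use that no passage prescribes. SAP 5.3 also requires an approved amendment for changes made before the primary analysis and disclosure of later ones, which limits a switch after the fact. At the planning values, mean filling would turn a fail into a pass in only about 1.3%, 3.3% and 6.7% of trials (2, 4 and 6 missing).

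Further points carry some weight. The sentence does not name the distance. MRI is described as required for radiotherapy patients, so few scans may be missing. LOCF is conservative against the goal and could serve as a labelled worst-case bound. A tipping-point analysis is allowed for functional success, which uses the same 7.5 mm.

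What these points do not remove is the problem under the benign reading. Mean filling still cannot challenge a pass. LOCF still gives one unlabelled extreme, with untreated anatomy entered as an observed result. A tipping point on a secondary proportion does not test a confidence limit for a mean.

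**Conclusion.** The concern holds and should be fixed. The wording conflict is an ambiguity to close, not evidence that the primary result will be imputed. The substantive defect is that the named methods cannot show how robust the distance result is.

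At the planning values, mean filling raises the lower limit by 0.31 mm (2 missing) to 1.08 mm (6 missing). LOCF leaves a pass with 2 or 3 missing. With 4 or more it falls on either side of 7.5 mm, depending on the pre-injection gap. These sizes rest on an assumed 2 to 6 missing of 20 and an assumed gap of 0 to 5 mm; the direction of the mean-filling effect rests on neither. The sample size is not in question.

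**What to change.** In SAP 4.3, delete the closing sentence and remove mean or median imputation for the distance. State that complete case on the SAP 4.1 efficacy set is the sole primary analysis.

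Pre-specify one sensitivity analysis in all subjects who received the device. It is a tipping-point analysis on the continuous distance in which the missing post-procedure values are lowered in fixed steps from the observed mean toward the pre-procedure distance. The variance must not treat imputed values as observed. Delta-adjusted multiple imputation combined by Rubin's rules is one programmable choice; the step size should be set in the SAP. Report the step at which the 95% lower limit crosses 7.5 mm. The pre-procedure distance then becomes the end of a range and not the only scenario.

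The cost is one deleted sentence, one clarified sentence and one extra table, made as an SAP amendment before the primary analysis, with no new data. The sponsor gives up a sensitivity result that would look more favourable than the new one may.
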